- To completely inform all participants in this study concerning the pertinent details and purpose of the study prior to their agreement to participate in the study in accordance with GCP and regulatory authority requirements.
- To be responsible for maintaining each participant's consent form in a secure study file and providing each participant with a signed copy of the consent form.
- That I am thoroughly familiar with the appropriate use of the investigational product(s), as described in the protocol, and any additional information provided to me by, or on behalf of AOBiome Therapeutics

Investigator Printed Name:		
G*	D 4	
Signature:	Date:	

Amendment 3 4

Statement of Compliance

The study will be carried out in accordance with Good Clinical Practice (GCP) as required by the following:

- United States (US) Code of Federal Regulations (CFR) applicable to clinical studies (45 CFR Part 46; 21 CFR Part 50, 21 CFR Part 56, and 21 CFR Part 312)
- ICH E6; 62 Federal Register 25691 (1997)

All key personnel (all individuals responsible for the design and conduct of this study) have completed Good Clinical Practice Training.

PROTOCOL AMENDMENT 3 SUMMARY OF CHANGES

Section	Description of Changes
Title Page	Updated with Sponsor's new company logo and
	business address
Sponsor Approval Page	Updated section with up to date information
Clinical Trial Summary	Per Administrative Letter dated 27FEB2018,
Section 6.2	Inclusion criteria for the study has been updated as
	follows: increase the upper limit of subject's BSA
	affected by Atopic Dermatitis to 30%.
Section 11.1	Per Administrative Letter dated 12MAR2018:
Schedule of Events Table	inserted clarification that that medical records
	from patient's dermatologist or primary care
	physician to confirm the diagnosis are optional.
	Verbal confirmation of the diagnosis present for ≥
	12 months is sufficient in order to fulfill this
	criterion.
Sections 7.2; 8.15.1; 11.6.2;	Per Administrative Letter dated 26APR2018,
Schedule of Events Table	inserted clarification language stating that the use
	of moisturizer in the study is not mandatory.
Sections 9; 11.6; 12.11	Per Administrative Letter dated 17JUL2018,
Schedule of Events Table	subjects will be provided with two (2) actigraphy
	watches at Baseline period and will be asked to
	wear one watch on each wrist at all times through
	Day 28. Subjects will be asked to return both
	watches at Day 28 visit.
Section 8.7	Modified language around IP kits
Section 12.1	Updated shipping schedule and corrected Lab
	name
Section 12.11	Updated Actigraphy watch schedule and
	procedures
Section 12.14	Revised language around sample shipment to state
	that samples will be shipped according to the Lab
	Manual.
Section 16.7	Updated safety reporting email

Administrative changes: Minor changes involving grammar, wordsmithing, punctuation, and other editorial changes have been made throughout the document. All are clearly identified in the track-changes version of the amendment.

Additional formatting and stylistic adjustments have been made to facilitate the reading process.

CLINICAL TRIAL SUMMARY

COMPOUND: B244 STUDY NUMBER: ADB244-001

TITLE:	A Prospective, Vehicle Controlled, Double Blind, Multicenter, Randomized, Phase II Study of B244 Delivered as a Topical Spray to Determine Safety in Subjects with Mild to Moderate Atopic Dermatitis.
INVESTIGATIONAL PRODUCT	B244 Topical application
STUDY ARMS	1. B244 2. Vehicle
PURPOSE:	The aim of the study is to assess the safety of B244 in the treatment of atopic dermatitis.
STUDY OBJECTIVES:	 Primary: To evaluate the safety and tolerability of B244 in participants with mild to moderate Atopic Dermatitis. Secondary: To assess the efficacy of B244 versus vehicle by the change in Atopic Dermatitis Area Severity Index (EASI) Score from Baseline to post-baseline visits
	Exploratory:

To assess the efficacy of B244 versus vehicle by the change in Visual Analog Scale (VAS) Score from Baseline to post-baseline visits To assess the efficacy of B244 versus vehicle by the change in Skindex 16 Score from Baseline to post-baseline visits To assess the efficacy of B244 versus vehicle by the change in Investigator Global Assessment Score (IGA) from Baseline to post-baseline visits To assess the efficacy of B244 versus vehicle by the change in Actigraphy Movement Count per Hour and sleep quality during nighttime from Baseline to postbaseline visits To evaluate if B244 administration on the skin twice daily for 28 days will affect the levels of immune biomarkers. To explore microbial content at baseline and Day 28. This is a Prospective, Vehicle Controlled, STUDY DESIGN: Double Blind, Multicenter, Randomized Phase II trial, comparing the effect of twice daily B244 application for 28 days vs vehicle application on treatment of mild to moderate AD At Screening and Baseline, all subjects must have atopic dermatitis, as defined by the Hanifin and Rajka criteria, which involves a minimum of 10% and a maximum of 30% body surface area, EASI score of 10 to 21 and pruritus visual analogue scale scores of ≥ 5 points on the

	VAS scale (at least moderate), IGA of 2-3.
	The total duration of the study will be approximately 9 weeks. Participants will report for a Screening visit and if all inclusion criteria are met, subjects will go through a two week washout phase before reporting for a Baseline visit.
	Subjects will come in for visits at Day 14 (Week 2), Day 28 (Week 4). A final visit will be conducted at Day 42 (Week 6).
	Efficacy will be assessed using Atopic Dermatitis Area and Severity Index (EASI), Visual Analog Scale (VAS) and Investigator Global Assessment (IGA) score.
	Blood and urine samples will be collected for standard safety laboratory tests and effect of the drug on inflammatory biomarkers. Participant's safety will be monitored throughout the study.
	We plan to enroll approximately 130 total patients. Assuming 20% drop out rate, we will plan to complete 104 patients.
	Randomization will be 1:1 so that equal number of patients will be treated in each Arm of the study.
	All B244 randomized subjects will be treated at the dose of 4x10 ⁹ cfu/ml (middose of the Phase 1b/2a safety trial)
STUDY POPULATION:	Male and female subjects 18 years of age or older with clinically diagnosed mild to moderate Atopic Dermatitis.
Main Inclusion Criteria:	 Male and female subjects ≥18 years of age

	In good general health as
	determined by a thorough medical history and physical examination, and vital signs
	Clinical diagnosis of mild to moderate atopic dermatitis according to the criteria of Hanifin and Rajka
	Mild to moderate Atopic Dermatitis area and severity index [EASI] 10-21
	 A score of at least ≥ 5 points (moderate pruritus) on the VAS for pruritus
	 A minimum of 10% and not more than 30% of the subjects' BSA affected by atopic dermatitis (affected is defined by physical examination findings: erythema, edema, scaling, lichenification, excoriation, with the excoriation serving as the physical examination correlate of pruritus) An IGA score of 2-3 Patient has a history of AD for ≥ 12 months Ability to read and understand English and to provide written informed consent and authorization for protected health information disclosure
Main Exclusion Criteria:	
	 Pregnant and lactating women by urine pregnancy testing Subjects with any significant clinical abnormalities which may interfere with study participation Any skin condition which may interfere with evaluation of AD Atopic dermatitis on the head or scalp

- Subjects with Atopic dermatitis on the face
- Unstable or actively infected atopic dermatitis
- Patients suffering from pruritus from conditions other than AD
- Patients with chronic pruritus due to systemic disease
- Patients with conditions requiring inhaled steroids
- Have concurrent skin disease of such severity in the study area that it could interfere with the study evaluation
- Have active skin infections on the treatment area
- Have received or planning to receive topical corticosteroids, topical coal tar, topical sulfur, topical PDE-4 inhibitors, topical antihistamines, topical antiseptics or antibiotics, topical antifungals, bleach baths, UVA or UVB phototherapy, oral/IV/inhaled steroids, antibiotics/antiviral/antifungal agents, oral probiotics, glucocorticoids treatment, calcineurin inhibitors, immunomodulating biologic agents, systemic glucocorticoids, systemic immunosuppressive or immunomodulatory agents within 2 weeks of Baseline visit.
- Current or recent history (≤ 3 months of systemic use of OtrexupTM, Rasuvo®,
 Rheumatrex® and TrexallTM or its generic versions such as Methotrexate
- History of being seropositive for human immunodeficiency virus (HIV) at screening by laboratory testing at Screening

	 History of being positive for Hepatitis B virus surface antigen (HBsAg) or positive Hepatitis C virus antibody (HCV Ab) at screening by laboratory testing at Screening History of renal disease Use of any investigational drugs within the previous 30 days prior to dosing or within a period of less than five times the drug's half-life, whichever is longer Use of any biologic within a period of 5 times its half-life Use of vinegar or bleach baths within 2 weeks of starting the study
DOSE REGIMEN:	Subjects will apply a total of 8 pumps of IP per application to all affected areas twice-a-day (i.e. 8 pumps in the morning and 8 pumps again at night) for 28 Days.
ASSESSMENT SCHEDULE:	All subjects will attend a screening visit not more than 21 days prior to Day 1. Subjects will be required to return to the clinic at Baseline, on Day 14 (Week 2), Day 28 (Week 4). All subjects will be asked to attend a follow-up visit 2 weeks (14 (±3) days) after the last dose of study medication.
STATISTICAL CONSIDERATIONS:	 All efficacy analyses will be performed on the ITT population and PP population The difference in treatment groups in change-from-baseline values at post-baseline visits will be analyzed using a mixed Analysis of Variance with one betweensubject variable (active group vs. vehicle group) and one within-

	subject variable One-sided two-sample equal-variance t-test will be performed as a supportive test to analyze the differences in treatment group means in change from baseline at each post-baseline visit
DURATION OF STUDY:	Subject's participation in the study will take up to 9 weeks. The estimated total study duration is 12 months. All subjects will be followed from enrollment and until the Final (End of Study Visit), which occurs 42 days following the baseline visit.

2 INTRODUCTION

2.1 Background

Ammonia oxidizing bacteria (AOB) are essential for the initial step in environmental nitrification processes, specifically the oxidation of ammonia (NH₃) to nitrite (NO₂-). *Nitrosomonas* are Gram-negative chemolithoautotrophic betaproteobacteria that obtain energy solely from NH₃ oxidation, while fixing CO₂ for their carbon needs. Oxidation of NH₃ proceeds in two steps (Figure 1) leading to sequential generation of hydroxylamine (NH₂OH) and NO₂- that require two enzyme complexes: the membrane-bound ammonia monooxygenase (AMO) comprised of subunits AmoA, AmoB and AmoC; and the periplasmic NH₂OH oxidoreductase (HAO). In addition to high NO₂- levels, NH₃ oxidation leads to nitric oxide (NO) and N₂O production through two independent pathways downstream of NH₂OH production: nitrifier denitrification and NH₂OH oxidation.²

Figure 1 Nitrifier Denitrification Pathway

B244 is a purified a strain of *Nitrosomonas eutropha* originally isolated from soil samples. Sequencing of the B244 genome revealed a distinct genetic profile from that of other published *Nitrosomonas* strains and AOB genomes. Based on *in vitro* co-culture studies, B244 was able to reduce survival of pathogenic bacteria. Nitrite generation from ammonia concurrently with medium acidification by B244 led to strong antibacterial effects and a marked reduction (~100-fold) in viable counts of methicillin-resistant *Staphylcoccus aureus* and *Pseudomonas aeruginosa*, two pathogens frequently isolated from infected skin and wound sites. In contrast, control cultures with B244 in the absence of ammonium or with heat-killed B244 supplemented with ammonium, had no antibacterial effects. The unique metabolic and antimicrobial activity of *Nitrosomonas*, in combination with their lack of virulence render these bacteria as attractive candidates for topical delivery of nitrite and nitric oxide on human skin with potential to improve health in both normal and abnormal skin conditions or wound sites. NO-releasing drugs or NO donors have also shown activity against *Propionibacterium acnes* and other pathogenic bacteria, anti-inflammatory activity, and inhibition of lipogenesis by insulin-stimulated immortal sebocytes.^{4,5}

B244 has been developed as a topical application of a natural source of AOB and NO/NOx to the human skin. We hypothesize that application of AOB to eczematous skin may reduce *S. aureus* skin load and normalize the inflammatory response by reducing Th2 activation.

Under IND #16487, a Phase 1b/2a clinical trial was completed in 2016 where 36 participants with clinical diagnosis of facial acne vulgaris were randomized to receive twice-daily ascending doses of B244 or Vehicle

over 14 days. All 3 dose levels of B244 were well tolerated and no safety issues were identified. There were no attributable drug related SAEs reported.

In addition, a Phase IIb/III clinical trial in 372 patients with clinical diagnosis of facial acne is currently ongoing that is assessing twice-daily application of B244 or Vehicle for 3 months. To date, there have been no treatment related SAEs reported in this trial.

Eczema or Atopic dermatitis is an inflammatory skin condition that affects nearly 20% of children and 2-10% of adults²⁰. Disease prevalence has steadily grown in the last 30 years, resulting in a growing field of atopic dermatitis reasearch²¹

The disease is characterized by pruritus, scratching, and eczematous lesions. The chronic condition may be associated with thickening and pigmentary changes. Onset of the disease occurs mostly between 3 and 6 months, but in 90% of children, the disease occurs by age of 5. Staphylococcus aureus is consistently found in eczematous skin lesions in patients with AD. Correlation between the severity of the disease and presence of Staphylococcus aureus has been well established and it has been shown that presence of bacteria is an important factor in skin aggravation²². The goal of therapy for AD is to restore the epidermal barrier function and reduce skin inflammation. However, systemic antibiotic use is controversial.

The primary purpose of this study is to evaluate the safety of B244 in treating patients with Atopic Dermatitis.

3 STUDY OBJECTIVES

3.1 Primary Objectives

• To evaluate the safety and tolerability of B244 in participants with mild to moderate Atopic Dermatitis.

3.2 Secondary Objectives

• To assess the efficacy of B244 versus vehicle by the change in Atopic Dermatitis Area Severity Index (EASI) Score from Baseline to post-baseline visits

3.3 Exploratory Objectives

- To assess the efficacy of B244 versus vehicle by the change in Visual Analog Scale (VAS) Score from Baseline to post-baseline visits
- To assess the efficacy of B244 versus vehicle by the change in Skindex 16 Score from Baseline to post-baseline visits
- To assess the efficacy of B244 versus vehicle by observing a change in the IGA score from Baseline to post-baseline visits
- To assess the efficacy of B244 versus vehicle by the change in Actigraphy Movement Count per Hour and sleep quality during nighttime from Baseline to post-baseline visits
- To evaluate if B244 administration on the skin twice daily for 28 days will affect the levels of immune biomarkers.
- To explore microbial content at baseline and Day 28.

4 ENDPOINTS

4.1 Safety & tolerability:

• Safety and tolerability endpoints will consist of all adverse events reporting during the study duration.

4.2 Efficacy:

Difference in Atopic Dermatitis Area Severity Index (EASI) Score from Baseline to Day 28

4.3 Exploratory:

- Difference in Visual Analog Scale (VAS) Score for Pruritus from Baseline to Day 28
- Difference in the Skindex 16 Score from Baseline to Day 28
- Difference in the IGA score from Baseline to Day 28
- Difference in Actigraphy Movement Count per Hour and sleep quality during the night from Baseline to Day 28
- Difference in biomarkers between active and vehicle groups
- Composition of microbiome
- Difference in skin microbiota from baseline to Day 28 between active and vehicle groups
 - Observing a difference in Staphylococcus aureus and a more diverse microbial collection on the patient's skin.

5 STUDY DESIGN

- This is a Prospective, Vehicle Controlled, Double Blind, Multicenter, Randomized Phase II trial, comparing the effect of twice daily B244 application for 28 days vs vehicle application on treatment of mild to moderate AD
- We will enroll approximately 130 patients and complete 104 patients
- After screening and recruitment, participants will be randomized to active or vehicle application for 28 days.
- Subjects will apply a total of 8pumps of IP per application to all affected areas twice-a-day (i.e. 8pumps in the morning and 8pumps again at night) for 28 days.
- Subjects will be provided with cleanser and moisturizer to use for the duration of the study
- Randomization will be 1:1 so that equal number of patients will be treated in each Arm of the study.
- All B244 randomized subjects will be treated at the dose of 4x10⁹ cfu/ml
- Screening will occur at Days -21 to -14
- Washout will occur after Screening visit (Days -14 to -1)
- Randomization will occur during the baseline period for the study
- Clinical assessments of response to treatment will be made at Baseline, Study Days 14 and 28.
- Subject will come back for the final visit on Study Day 42
- Safety evaluations will consist of review of participant's medical history at screening and on-going assessment of adverse events reported throughout the study duration.

6 SELECTION OF STUDY PARTICIPANTS

6.1 Number of Participants Planned

It is estimated that approximately 130 participants will be consented in order to provide 104 completed participants for randomization, treatment, and inclusion in the primary analysis.

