15 STATISTICAL CONSIDERATIONS

15.1 Sample Size

A total sample size of 130 randomized subjects, allows for a dropout rate of 20%.

A sample size of 52 per group achieves >80% power to reject the null hypothesis of equal means when the population mean difference is $\mu 1 - \mu 2 = (-1.4) - (-5.3) = 3.9$ with a standard deviation for both groups of 7.0 and with a significance level (alpha) of 0.025 using a one-sided two-sample equal-variance t-test.

The power calculation assumes baseline treatment group means of 14 in EASI score. The change from baseline to Day 28 is assumed to be -1.4 for the vehicle group and -5.3 for the active group; this represents about 38% reduction in EASI score for the active group and 10% reduction in EASI score for the placebo group.

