### 1.2. Study Design

### 1.2.1. Synopsis of Study Design

This is a prospective, vehicle controlled, double blind, multicenter, randomized Phase II trial comparing the effect of twice daily B244 application for 28 days versus vehicle application on treatment of mild to moderate AD.

Subjects who have clinically confirmed diagnosis of mild to moderate AD are eligible for enrollment. Subjects must be in general good health as determined by a thorough medical history, physical examination, and vital signs.

It is estimated that approximately 130 subjects will be randomized in order to provide 104 subjects for inclusion in the primary analysis, assuming a 20% drop-out rate.

After screening and recruitment, subjects will be randomized 1:1 to B244 or vehicle application for 28 days. Subjects will apply a total of 8 pumps of investigational product (IP) per application to all affected areas twice-a-day for 28 days.

[figure not shown]
Clinical assessments of response to treatment will be made at Baseline, Study Days 14 and 28. Subject will come back for the final visit on Study Day 42.

Safety evaluations will consist of review of subject's medical history at screening and on-going assessment of adverse events reported throughout the study duration.

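### Protocol 6.1 gives 130 as the number consented and 104 as the number for randomization; Protocol 15.1 and the SAP need 130 randomized, so the planned count in 6.1 is wrong as written.

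*Protocol*

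**What the plan says.** The documents attach the numbers 130 and 104 to different stages of the trial.

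- Protocol 6.1 (Number of Participants Planned): "approximately 130 participants will be consented in order to provide 104 completed participants for randomization". The sentence goes on to treatment and inclusion in the primary analysis.
- Protocol 15.1 (Sample Size), repeated in SAP 3.1: "A total sample size of 130 randomized subjects, allows for a dropout rate of 20" per cent.
- SAP 1.2.1 (Synopsis of Study Design): "approximately 130 subjects will be randomized in order to provide 104 subjects for inclusion in the primary analysis", assuming 20% drop-out.
- Protocol synopsis and Section 5: about 130 are to be enrolled and 104 are to complete. The synopsis links the two by a 20% dropout rate.

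The power statement that these counts support is in Protocol 15.1: "A sample size of 52 per group achieves >80% power to reject the null hypothesis of equal means".

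**The concern.** Section 6.1 is the part of the protocol headed as the planned number of participants, and it puts the loss from 130 to 104 between consent and randomization. Everywhere that the sample size is justified, the same loss falls after randomization.

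Consented and randomized are different counts in this trial. Consent precedes every study-specific procedure (Protocol 7.1, 11.2). Screening laboratory tests, a two-week washout and a repeat check of eligibility at Baseline follow (7.2, 11.6.2, 11.6.3), and Section 7.4 expects both screen and baseline failures.

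The stated power has almost no slack: it needs all 52 per arm with data, and missing values are not imputed (Protocol 15.4.6). If 104 became the randomization target, nothing would cover loss after randomization. Subjects who need rescue medication are discontinued as early terminations (Protocol 8.14), so some loss is built into the design.

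**Working it through.** **Inputs, all from Protocol 15.1 unless noted.**

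- Difference 3.9 EASI points: "The change from baseline to Day 28 is assumed to be -1.4 for the vehicle group and -5.3 for the active group", so −1.4 − (−5.3) = 3.9.
- SD 7.0: "with a standard deviation for both groups of 7.0".
- Test: "with a significance level (alpha) of 0.025 using a one-sided two-sample equal-variance t-test".
- Allocation 1:1 (Protocol 5): "Randomization will be 1:1 so that equal number of patients will be treated in each Arm of the study".
- Dropout 20%, applied to randomized subjects.

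**Step 1. Reproduce the plan's figures.** Power = P(T > t₀.₉₇₅,df), where T is noncentral t with df = n₁ + n₂ − 2 and noncentrality δ / [σ√(1/n₁ + 1/n₂)].

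- 52 per arm: standard error 7.0 × √(2/52) = 1.373; noncentrality 3.9/1.373 = 2.841; df 102; power **80.3%**. At 51 per arm power is 79.6%, so 52 is the smallest number per arm that passes 80%.
- Inflation for dropout: 104/(1 − 0.20) = **130**, or 65 per arm.

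Both figures in 15.1 are confirmed.

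**Step 2. Set the counts side by side.**

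| Source | What 130 counts | What 104 counts |
|---|---|---|
| Protocol 6.1 | consented | completed, for randomization, treatment and analysis |
| Protocol 15.1, SAP 3.1 | randomized | not named; 2 × 52 = 104 remain after 20% dropout |
| SAP 1.2.1 | randomized | in the primary analysis |
| Protocol synopsis, Section 5 | enrolled | completed |

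Protocol 13.3 defines a completed participant as one who has made every visit, the last being Day 42. Completed participants therefore cannot be supplied for randomization, and 6.1 contradicts itself as well as 15.1.

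The word enroll does not settle the matter. Protocol 15.4.6 and SAP 3.9 speak of dropping out after enrollment but before randomization, and SAP Table 14.1.1 has separate rows for enrolled and randomized.

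**Step 3. What follows if 104 is taken as the randomization target.** With the planned 20% dropout, 104 × 0.80 = 83.2 remain, about 42 and 41 per arm. Standard error 7.0 × √(1/42 + 1/41) = 1.537; noncentrality 3.9/1.537 = 2.538; df 81; power **70.8%**.

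Power with 104 randomized, by loss after randomization (equal arms, fractional numbers kept):

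| Loss | Analysed | Power |
|---|---|---|
| 0% | 104 | 80.3% |
| 5% | 98.8 | 78.3% |
| 10% | 93.6 | 76.0% |
| 15% | 88.4 | 73.6% |
| 20% | 83.2 | 70.9% |

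**Step 4. Illustration only.** Suppose that 130 were a ceiling on consents and that 20% of those randomized then dropped out. Assumed screen-failure rates of 10%, 30% and 40% would give 76.0%, 65.0% and 58.1%. The documents state no screen-failure rate, so these rates are assumptions.

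**The case against.** The strongest reply is that 6.1 is one badly worded sentence and the intended plan is clear. The sample-size section and SAP 3.1 both say 130 randomized, and SAP 1.2.1 carries nearly the same sentence as 6.1 with the right verb. The documents plan a single 20% loss; the 71% takes it once before randomization and again after. Section 6.1 also attaches the word completed to the 104, and if 104 do complete and are analysed, power stays at 80.3%.

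Much of this stands. A reader might infer that the trial is underpowered, or that power will be 71% or less. The documents do not support that:

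- The calculation in 15.1 is correct and 130 randomized are already planned.
- Section 6.1 gives an estimate and sets no cap on consents.
- Subjects lost after enrollment but before randomization are replaced (Protocol 15.4.6, SAP 3.9). This suggests that early losses were not meant to shrink the randomized number. Whether the rule covers screen failures depends on what enrollment means.
- Power below 71% needs either an assumed screen-failure rate together with a cap, or dropout above the planned 20%.

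The stakes are also limited. The primary objective is safety and tolerability, EASI is secondary, and Protocol 15.4.5 has the efficacy p-values read as exploratory.

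What the reply does not remove is the contradiction. It is in current text, in the section that states the planned number. The replacement rule does not say whether 104 or 130 is the randomization target, and the word completed makes 6.1 impossible in sequence.

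**Conclusion.** The point holds as an internal inconsistency in the stated sample size. It is not an arithmetic error: 52 per arm, 80.3% power and 130 randomized all check. Section 6.1 is wrong as written and conflicts with Protocol 15.1, SAP 3.1 and SAP 1.2.1.

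The possible cost is conditional. If 104 were randomized and the planned 20% then dropped out, power for the secondary EASI comparison would be about 71%, roughly nine to ten points below plan. With less loss it would lie between 71% and 80%. This rests on the plan's own difference of 3.9, SD of 7.0 and one-sided 0.025 t-test. The screen-failure figures are illustrations and should not be read as a forecast.

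**What to change.** Reword Protocol 6.1 along these lines:

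> About 130 participants will be randomized (65 per arm) to leave about 104 for the Day 28 EASI analysis, assuming 20% dropout. Enough participants will be consented and screened to reach this number.

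In Section 5 and the synopsis, use randomize instead of enroll for the 130. SAP 1.2.1 and 3.1 need no change.

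The cost is a protocol wording change. It adds no randomized participants to those already planned in 15.1 and the SAP, and no analysis changes.
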